**Table 22: Vital Sign at Screening**

	All (N = 120)	COVIVAC				Placebo (N = 20)
		1 µg (N = 25)	3 µg (N = 25)	10 µg (N = 25)	1 µg + CpG (N = 25)	
Systolic blood pressure (mmHg)						
n	xx	xx	xx	xx	xx	xx
Mean (SD)	xx.xx (xx.xx)	xx.xx (xx.xx)	xx.xx (xx.xx)	xx.xx (xx.xx)	xx.xx (xx.xx)	xx.xx (xx.xx)
Median (q1-q3)	xx (xx-xx)	xx (xx-xx)	xx (xx-xx)	xx (xx-xx)	xx (xx-xx)	xx (xx-xx)
Min-Max	xx-xx	xx-xx	xx-xx	xx-xx	xx-xx	xx-xx
Diastolic blood pressure (mmHg)						
n	xx	xx	xx	xx	xx	xx
Mean (SD)	xx.xx (xx.xx)	xx.xx (xx.xx)	xx.xx (xx.xx)	xx.xx (xx.xx)	xx.xx (xx.xx)	xx.xx (xx.xx)
Median (q1-q3)	xx (xx-xx)	xx (xx-xx)	xx (xx-xx)	xx (xx-xx)	xx (xx-xx)	xx (xx-xx)
Min-Max	xx-xx	xx-xx	xx-xx	xx-xx	xx-xx	xx-xx
Pulse rate (beats /min.)						
n	xx	xx	xx	xx	xx	xx
Mean (SD)	xx.xx (xx.xx)	xx.xx (xx.xx)	xx.xx (xx.xx)	xx.xx (xx.xx)	xx.xx (xx.xx)	xx.xx (xx.xx)
Median (q1-q3)	xx (xx-xx)	xx (xx-xx)	xx (xx-xx)	xx (xx-xx)	xx (xx-xx)	xx (xx-xx)
Min-Max	xx-xx	xx-xx	xx-xx	xx-xx	xx-xx	xx-xx
Respiratory rate (breaths/min.)						
n	xx	xx	xx	xx	xx	xx
Mean (SD)	xx.xx (xx.xx)	xx.xx (xx.xx)	xx.xx (xx.xx)	xx.xx (xx.xx)	xx.xx (xx.xx)	xx.xx (xx.xx)
Median (q1-q3)	xx (xx-xx)	xx (xx-xx)	xx (xx-xx)	xx (xx-xx)	xx (xx-xx)	xx (xx-xx)
Min-Max	xx-xx	xx-xx	xx-xx	xx-xx	xx-xx	xx-xx

**Table 22: Vital Sign at Screening (continued)**

	All (N = 120)	COVIVAC				Placebo (N = 20)
		1 µg (N = 25)	3 µg (N = 25)	10 µg (N = 25)	1 µg + CpG (N = 25)	
Temperature (°C)						
n	xx	xx	xx	xx	xx	xx
Mean (SD)	xx.xx (xx.xx)	xx.xx (xx.xx)	xx.xx (xx.xx)	xx.xx (xx.xx)	xx.xx (xx.xx)	xx.xx (xx.xx)
Median (q1-q3)	xx (xx-xx)	xx (xx-xx)	xx (xx-xx)	xx (xx-xx)	xx (xx-xx)	xx (xx-xx)
Min-Max	xx-xx	xx-xx	xx-xx	xx-xx	xx-xx	xx-xx
Route						
Oral	xx (xx.x%)	xx (xx.x%)	xx (xx.x%)	xx (xx.x%)	xx (xx.x%)	xx (xx.x%)
Other	xx (xx.x%)	xx (xx.x%)	xx (xx.x%)	xx (xx.x%)	xx (xx.x%)	xx (xx.x%)
...	xx (xx.x%)	xx (xx.x%)	xx (xx.x%)	xx (xx.x%)	xx (xx.x%)	xx (xx.x%)

**Note:** + CpG1018 1.5 mg (Adjuvant)

“xx” represent the value number.

**Table 23: Physical Examination at Screening**

	All (N = 120)	COVIVAC				Placebo (N = 20)
		1 µg (N = 25)	3 µg (N = 25)	10 µg (N = 25)	1 µg + CpG (N = 25)	
General Appearance, n (%)						
Normal	xx (xx.x %)	xx (xx.x %)	xx (xx.x %)	xx (xx.x %)	xx (xx.x %)	xx (xx.x %)
Abnormal	xx (xx.x %)	xx (xx.x %)	xx (xx.x %)	xx (xx.x %)	xx (xx.x %)	xx (xx.x %)
Clinically sig**	xx (xx.x %)	xx (xx.x %)	xx (xx.x %)	xx (xx.x %)	xx (xx.x %)	xx (xx.x %)
Not done	xx (xx.x %)	xx (xx.x %)	xx (xx.x %)	xx (xx.x %)	xx (xx.x %)	xx (xx.x %)
HEENT, n (%)						
Normal						
Abnormal						
Clinically sig**						
Not done						
Cardiovascular, n (%)						
Normal						
Abnormal						
Clinically sig**						
Not done						
Respiratory, n (%)						
Normal						
Abnormal						
Clinically sig**						
Not done						
Abdomen, n (%)						
Normal						
Abnormal						
Clinically sig**						
Not done						

**Table 23: Physical Examination at Screening (continued)**

	COVIVAC					Placebo (N = 20)
	All (N = 120)	1 µg (N = 25)	3 µg (N = 25)	10 µg (N = 25)	1 µg + CpG (N = 25)	
Musculoskeletal, n (%)						
Normal						
Abnormal						
Clinically sig**						
Not done						
Extremity/Skin, n (%)						
Normal	xx (xx.x %)	xx (xx.x %)	xx (xx.x %)	xx (xx.x %)	xx (xx.x %)	xx (xx.x %)
Abnormal	xx (xx.x %)	xx (xx.x %)	xx (xx.x %)	xx (xx.x %)	xx (xx.x %)	xx (xx.x %)
Clinically sig**						
Not done	xx (xx.x %)	xx (xx.x %)	xx (xx.x %)	xx (xx.x %)	xx (xx.x %)	xx (xx.x %)
Neurological, n (%)						
Normal						
Abnormal						
Clinically sig**						
Not done						
Lymph Nodes, n (%)						
Normal						
Abnormal						
Clinically sig**						
Not done						
Other, n (%)						
....						

**Note:** + CpG1018 1.5 mg (Adjuvant)

“xx” represent the value number.

\*\* Abnormal result clinically significant

**Table 24: Hematology Test at Screening**

	All (N = 120)	COVIVAC				Placebo (N = 20)
		1 µg (N = 25)	3 µg (N = 25)	10 µg (N = 25)	1 µg + CpG (N = 25)	
Hemoglobin (g/dL)						
n	xx	xx	xx	xx	xx	xx
Mean (SD)	xx.xx (xx.xx)	xx.xx (xx.xx)	xx.xx (xx.xx)	xx.xx (xx.xx)	xx.xx (xx.xx)	xx.xx (xx.xx)
Median (q1-q3)	xx (xx-xx)	xx (xx-xx)	xx (xx-xx)	xx (xx-xx)	xx (xx-xx)	xx (xx-xx)
Min-Max	xx-xx	xx-xx	xx-xx	xx-xx	xx-xx	xx-xx
White Blood Cell (WBC) (x 10^3/µL)						
n						
Mean (SD)						
Median (q1-q3)						
Min-Max						
Platelets (x 10^3/µL)						
n						
Mean (SD)						
Median (q1-q3)						
Min-Max						

**Note:** + CpG1018 1.5 mg (Adjuvant)

“xx” represent the value number.

**Table 25: Abnormality of Hematology Test with Clinically Significant Result at Screening**

	All (N = 120)	COVIVAC				Placebo (N = 20)
		1 µg (N = 25)	3 µg (N = 25)	10 µg (N = 25)	1 µg + CpG (N = 25)	
		n (%)	n (%)	n (%)	n (%)	
Hemoglobin (g/dL)	xx (xx.x%)	xx (xx.x%)	xx (xx.x%)	xx (xx.x%)	xx (xx.x%)	xx (xx.x%)
White Blood Cell (WBC) (x 10  /µL)						
Platelets (x 10  /µL)						

**Note:** + CpG1018 1.5 mg (Adjuvant)

“xx” represent the value number.

Only subjects with abnormality of hematology result will be considered in this table.

**Table 26: Chemistry Test at Screening**

	All (N = 120)	COVIVAC				Placebo (N = 20)
		1 µg (N = 25)	3 µg (N = 25)	10 µg (N = 25)	1 µg + CpG (N = 25)	
Creatinine (mg/dL)						
n	xx	xx	xx	xx	xx	xx
Mean (SD)	xx.xx (xx.xx)	xx.xx (xx.xx)	xx.xx (xx.xx)	xx.xx (xx.xx)	xx.xx (xx.xx)	xx.xx (xx.xx)
Median (q1-q3)	xx (xx-xx)	xx (xx-xx)	xx (xx-xx)	xx (xx-xx)	xx (xx-xx)	xx (xx-xx)
Min-Max	xx-xx	xx-xx	xx-xx	xx-xx	xx-xx	xx-xx
ALT (U/L)						
n						
Mean (SD)						
Median (q1-q3)						
Min-Max						
AST (U/L)						
n						
Mean (SD)						
Median (q1-q3)						
Min-Max						
Total bilirubin (mg/dL)						
n						
Mean (SD)						
Median (q1-q3)						
Min-Max						

**Note:** + CpG1018 1.5 mg (Adjuvant)

“xx” represent the value number.

**Table 27: Abnormality of Chemistry Test with Clinically Significant Result at Screening**

	All (N = 120)	COVIVAC					Placebo (N = 20)
		1 µg (N = 25)	3 µg (N = 25)	10 µg (N = 25)	1 µg + CpG (N = 25)		
		n (%)	n (%)	n (%)	n (%)		
Creatinine (mg/dL)	xx (xx.x%)	xx (xx.x%)	xx (xx.x%)	xx (xx.x%)	xx (xx.x%)	xx (xx.x%)	xx (xx.x%)
ALT (U/L)							
AST (U/L)							
Total bilirubin (mg/dL)							

**Note:** + CpG1018 1.5 mg (Adjuvant)

“xx” represent the value number.

Only subjects with abnormality of chemistry result will be considered in this table.

**Table 28: Viral Serology Result at Screening**

	All (N = 120)	COVIVAC				Placebo (N = 20)
		1 µg (N = 25)	3 µg (N = 25)	10 µg (N = 25)	1 µg + CpG (N = 25)	
HBsAg						
Positive						
Negative						
Not done						
N/A						
HCV Ab						
Positive						
Negative						
Not done						
N/A						

**Note:** + CpG1018 1.5 mg (Adjuvant)  
 “xx” represent the value number.

## Appendix 1.B. Reactogenicity - Local Reactions

**Table 29: Local Reaction at 30 minutes after Vaccination in Safety Analysis Population**

Reaction		COVIVAC					Placebo (N = 20)
		All (N = 120)	1 µg (N = 25)	3 µg (N = 25)	10 µg (N = 25)	1 µg + CpG (N = 25)	
		n (%) (95% CI*)					
Pain OR Tenderness	1 st Dose	xx (xx.x%) (xx.x-xx.x)					
	p-value=	x.XXXX					
	2 nd Dose	xx (xx.x%) (xx.x-xx.x)					
	p-value=	x.XXXX					
Swelling OR Induration	1 st Dose	xx (xx.x%) (xx.x-xx.x)					
	p-value=	x.XXXX					
	2 nd Dose	xx (xx.x%) (xx.x-xx.x)					
	p-value=	x.XXXX					
Erythema	1 st Dose	xx (xx.x%) (xx.x-xx.x)					
	p-value=	x.XXXX					
	2 nd Dose	xx (xx.x%) (xx.x-xx.x)					
	p-value=	x.XXXX					

**Note:** \*Two-sided 95% CIs computed via the Clopper-Pearson method  
Comparing overall dose levels; P-value based on Chi-square test

**Table 30: Local Reaction by Severity within 30 minutes after Vaccination in Safety Analysis Population**

	All (N = 120)	COVIVAC				Placebo	
		1 µg (N = 25)	3 µg (N = 25)	10 µg (N = 25)	1 µg + CpG (N = 25)		
		n (%) (95% CI*)	n (%) (95% CI*)	n (%) (95% CI*)	n (%) (95% CI*)		
Pain OR Tenderness							
1st Dose							
None	xx (xx.x%) (xx.x-xx.x)						
Mild	xx (xx.x%) (xx.x-xx.x)						
Moderate	xx (xx.x%) (xx.x-xx.x)						
Severe	xx (xx.x%) (xx.x-xx.x)						
Potentially life-threatening	xx (xx.x%) (xx.x-xx.x)						

p-value = x.xxxx

**2nd Dose**

None

Mild

Moderate

Severe

Potentially life-threatening

p-value =

**Table 30: Local Reaction by Severity within 30 minutes after Vaccination in Safety Analysis Population (continued)**

Reaction	All (N = 120)	COVIVAC				Placebo
	n (%)	1 µg (N = 25)	3 µg (N = 25)	10 µg (N = 25)	1 µg + CpG (N = 25)	n (%)
	(95% CI*)	(95% CI*)	(95% CI*)	(95% CI*)	(95% CI*)	(95% CI*)
Swelling OR Induration						
1st Dose						
None						
Mild						
Moderate						
Severe						
Potentially life-threatening						
p-value =						
2nd Dose						
None						
Mild						
Moderate						
Severe						
Potentially life-threatening						
p-value =						

**Table 30: Local Reaction by Severity within 30 minutes after Vaccination in Safety Analysis Population (continued)**

Reaction	COVIVAC					Placebo
	All (N = 120)	1 µg (N = 25)	3 µg (N = 25)	10 µg (N = 25)	1 µg + CpG (N = 25)	(N = 20)
	n (%) (95% CI*)	n (%) (95% CI*)				

**Erythema****1st Dose**

None

Mild

Moderate

Severe

Potentially life-threatening

p-value =

**2nd Dose**

None

Mild

Moderate

Severe

Potentially life-threatening

p-value =

**Note:** \*Two-sided 95% CIs computed via the Clopper-Pearson method  
Comparing overall dose levels; P-value based on Chi-square test;

**Table 31: Local Reaction Started During Day 1 - Day 7 after Vaccination in Safety Analysis Population**

Reaction	All (N = 120)	COVIVAC				Placebo (N = 20)
		1 µg (N = 25)	3 µg (N = 25)	10 µg (N = 25)	1 µg + CpG (N = 25)	
		n (%) (95% CI*)	n (%) (95% CI*)	n (%) (95% CI*)	n (%) (95% CI*)	
Pain OR Tenderness	1 st Dose	xx (xx.x%) (xx.x-xx.x)				
	p-value=	x.XXXX				
	2 nd Dose					
		p-value=				
Swelling OR Induration	1 st Dose					
	p-value=					
	2 nd Dose					
		p-value=				
Erythema	1 st Dose					
	p-value=					
	2 nd Dose					
		p-value=				

**Note:** \*Two-sided 95% CIs computed via the Clopper-Pearson method  
Comparing overall dose levels; P-value based on Chi-square test

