## 3.2. Study Endpoints

### 3.2.1. Primary Endpoints

#### Safety and Tolerability

- Number and severity of solicited local and systemic AEs during the first 7 days after each vaccination
- Number, severity, and relatedness of clinically significant hematological and biochemical measurements at 7 days post each vaccination
- Number, severity and relatedness of all unsolicited AEs during the first 28 days after each vaccination
- Number, severity and relatedness of SAEs throughout the entire study period
- Number, severity and relatedness of MAAEs throughout the entire study period
- Number, severity and relatedness of AESI throughout the entire study period, including AESI relevant to COVID-19, and potential immune-mediated medical conditions (PIMMC)

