#### **4.4. Method of Assigning Participants to Treatment Groups (Randomization)**

The randomization scheme was generated and maintained by Center of Excellence for Biomedical and Public Health Informatics (BIOPHICS).

Randomization for Part 1 (Phase 1) will be conducted after accumulation of 120 eligible subjects. Randomization will be stratified by gender and age (less than 40 years old and 40 to 59 years old, with approximately 50% of subjects in each age stratum). This is to ensure the groups are as similar (homogenous) as possible to ensure the down-selection of formulations is not biased by differences in demographic characteristics of the groups (such as age and gender). Randomization details will be outlined in a Randomization Plan prior to study initiation.

Each group will be divided into two subgroups, a sentinel subgroup (n=6) and a larger subgroup (n=24) that includes the remaining subjects to be evaluated at that dose level (or for that formulation in the case of the one adjuvanted treatment group). Initially, a sentinel subgroup of 6 subjects will be randomized to receive NDV-HXP-S 1  $\mu$ g or placebo in a 5:1 ratio. Sentinel subjects will be monitored for reactogenicity and safety through Day 8 (Visit 2), including for the initial 24 hours post-injection in clinic. If the PSRT has no safety concerns based on blinded review of all safety data, including clinical laboratory results, through Visit 2, the second subgroup of 24 subjects will be randomized to receive NDV-HXP-S 1  $\mu$ g or placebo at the same ratio; on the same day, the sentinel subgroup (n=6) for the second dose level to be evaluated (NDV-HXP-S 3  $\mu$ g) can be randomized to receive study vaccine or placebo in a 5:1 ratio, and so on for the subsequent dose level and formulation (see [Table 2](#)). The same procedure will be used for the NDV-HXP-S 10  $\mu$ g and NDV-HXP-S 1  $\mu$ g + CpG arms for a total of n=25 in each active group and n=20 in the placebo group. Randomization will be stratified by age (less than 40 years old and 40 to 59 years old) and gender with approximately 25% of subjects in each age & gender stratum.

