### 8.3. Adverse Events

All safety assessment will take place in the safety analysis population, according to the treatment received. All subject-level percentages (solicited/unsolicited AEs, clinical safety laboratory abnormalities, etc.) will be supplemented with two-sided 95% CIs computed via the Clopper-Pearson method. Individual summaries (denominators for percentages) will be limited to the number of subjects with the appropriate analysis population with the data available for analysis for the given endpoint. Summaries will be provided overall by group and by stage ([Table 39](#), [Table 41](#), [Table 42](#), [Table 60](#), [Table 64](#)).

The non-serious adverse events from combined solicited and unsolicited (excluding serious adverse event) that being reported during the first 28 days after each vaccination will be summarized with the number of subject by vaccination groups. This combined data will be summarized by System Organ Class (SOC) and Preferred Term (PT) also ([Table 39](#) and [Table 40](#)).

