#### 8.3.1. Solicited Events and Symptoms

Solicited local and systemic adverse events: Percentages of subjects experiencing each solicited AE within 30 minutes observation period and during the first 7 days after each dose vaccination

will be presented for each symptom ([Table 29](#), [Table 31](#), [Table 34](#), [Table 36](#)). All solicited AEs will also be summarized according to defined severity grading scales ([Table 30](#), [Table 32](#), [Table 35](#), [Table 37](#)). Comparison of solicited AE of different dose levels will be done for overall dose, first dose and second dose of each symptom. Data listings of all solicited AEs will be provided by subject ([Listing 7](#)).

Clinically significant hematological and biochemical measurements: For clinical safety laboratory data collected at screening and 7 days post-first administration of study product (Visit 2, Day 8) and post-second administration of study product (Visit 4, Day 36), individual Hgb, WBC count, Plt, AST, ALT, total bilirubin, and creatinine values will be presented as number of subjects out of range (above and below normal range as appropriate) and tabulated by toxicity grading, relatedness, and study group ([Table 60](#) through [Table 68](#)). In addition, mean percentage changes from baseline (95% CI) will be presented. Plot of laboratory results evaluated both pre, post-first and second vaccination will be presented ([Appendix 2.B.- Figure 2](#) through [Figure 8](#)).

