## 8.6. Clinical Laboratory Evaluations

Screening viral serology assessments for Hepatitis B (HBsAg) and Hepatitis C (HCV Ab) will be described as categorical variables on a demographics table ([Table 28](#)).

Clinical safety laboratory values (serum hematology and chemistry) are collected at screening and 7 days post-vaccination for each dose. They will be summarized for the safety analysis population. Hematology and chemistry results evaluated at screening will be summarized as continuous variables by vaccine groups ([Table 24](#) through [Table 27](#)).

Screening and post-vaccination (Day 8 and Day 36) serum hematology and chemistry will be graded by severity. Grade 2 or higher were automatically considered as clinically significant and reported as AE, while Grade 1 abnormalities were subject to investigator opinion.

Continuous summaries of laboratory parameters (Hgb, WBC count, Plt, AST, ALT, total bilirubin, and creatinine) and the change from baseline will be computed by time point (including unscheduled visits, in chronological order) and treatment group, including mean, standard deviation, median, 1st and 3rd quartiles (IQR) and range, for all observations regardless of abnormality status (see [Table 60](#) through [Table 68](#)). Summaries will also be produced presenting the proportion of each severity grading using the number of subjects that provided a sample as denominator, as well as those considered clinically significant, using the maximum severity for a given subject, where relevant. A summary of safety laboratory abnormalities will be prepared by parameter, severity (by grade and any abnormality), and time point. Fisher's exact 2-tailed test will be used to test the differences in abnormality rates across all groups, by time point for scheduled visits, and overall.

Figures will be prepared for each laboratory parameter using boxplots to describe the distribution of values and changes from baseline across visits, by group, incorporating unique points and/or colors for abnormalities ([Figure 2](#) through [Figure 8](#)).

A listing of all lab results will be prepared, in addition to a listing only for abnormalities, and each will include the parameter, study day (Visit), value, units, change from baseline, LLN/ULN, and abnormality grade ([Listing 9A](#), [Listing 9B](#), Appendix 3).

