**2nd Dose**

None

Mild

Moderate

Severe

Potentially life-threatening

p-value =

**Note:** \*Two-sided 95% CIs computed via the Clopper-Pearson method  
Comparing overall dose levels; P-value based on Fisher's exact test

**Table 33: Incidence of New Onset and Ongoing Local Reaction Reported on each Day During Day 1- Day 7 after Vaccination in Safety Analysis Population**

Reaction		All (N = 120)	COVIVAC				Placebo (N = 20)
		1 µg (N = 25)	3 µg (N = 25)	10 µg (N = 25)	1 µg + CpG (N = 25)		
		n (%) (95% CI*)	n (%) (95% CI*)	n (%) (95% CI*)	n (%) (95% CI*)		
Pain OR Tenderness	1st Dose						
	Day 1						
	Day 2						
	Day 3						
	.....						
	Day 7						
	2nd Dose						
	Day 1						
	Day 2						
	Day 3						
	.....						
	Day 7						
Swelling OR Induration	1st Dose						
	Day 1						
	Day 2						
	Day 3						
	.....						
	Day 7						
	2nd Dose						
	Day 1						
	Day 2						
	Day 3						
	.....						
	Day 7						

**Table 33: Incidence of New Onset and Ongoing Local Reaction Reported on each Day During Day 1- Day 7 after Vaccination in Safety Analysis Population (continued)**

Reaction	All (N = 120)	COVIVAC				Placebo (N = 20)
		1 µg (N = 25)	3 µg (N = 25)	10 µg (N = 25)	1 µg + CpG (N = 25)	
		n (%) (95% CI*)	n (%) (95% CI*)	n (%) (95% CI*)	n (%) (95% CI*)	
Erythema	1st Dose					
	Day 1					
	Day 2					
	Day 3					
	.....					
	Day 7					
	2nd Dose					
	Day 1					
	Day 2					
	Day 3					
	.....					
	Day 7					

**Note:** Comparing overall dose levels; P-value based on Chi-square test.

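### Five solicited-reaction tables use an asymptotic chi-square test in arms of 25 and 20, against the exact test in their parallel tables, and the comparison of dose levels ignores dose order

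*SAP*

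**What the plan says.** Section 3.2.1 lists first among the primary endpoints: "Number and severity of solicited local and systemic AEs during the first 7 days after each vaccination". Section 4.4 gives the arm sizes, "for a total of n=25 in each active group and n=20 in the placebo group". Section 8.3.1 plans the comparison without naming a test: "Comparison of solicited AE of different dose levels will be done for overall dose, first dose and second dose of each symptom". The test is fixed only in the notes under the table shells in Appendices 1.B and 1.C:

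| Table | Content | Test in the note |
|---|---|---|
| 29 | local, 30 minutes, yes/no | chi-square |
| 30 | local, 30 minutes, by severity | chi-square |
| 31 | local, days 1-7, yes/no | chi-square |
| 32 | local, days 1-7, by severity | Fisher's exact |
| 34 | systemic, 30 minutes, yes/no | chi-square |
| 35 | systemic, 30 minutes, by severity | Fisher's exact |
| 36 | systemic, days 1-7, yes/no | chi-square |
| 37 | systemic, days 1-7, by severity | Fisher's exact |

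The two notes are "Comparing overall dose levels; P-value based on Chi-square test" and "Comparing overall dose levels; P-value based on Fisher's exact test". Table 33 carries the chi-square note too, but its shell has no p-value row. For laboratory abnormalities Section 8.6 says "Fisher's exact 2-tailed test will be used to test the differences in abnormality rates across all groups". Safety percentages "will be supplemented with two-sided 95% CIs computed via the Clopper-Pearson method" (Section 8.3), so exact intervals stand beside the chi-square p-values. The shells have rows for the first and second dose only. No trend test or dose score appears. Nothing says whether placebo and the CpG arm enter the comparison.

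**The concern.** There are three faults.

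1. **The choice of test is not consistent.** Table 30 and Table 35 are the same severity analysis at 30 minutes, one local and one systemic, yet they use different tests.
2. **The chi-square approximation is weak where reactions are infrequent.** A cluster of two or three events in one formulation is the kind of result a safety reader looks at, and there the printed p-value can be about half the exact one. Section 6.6.1 puts Tables 29, 31, 34 and 36 in the interim report and leaves out Tables 32, 35 and 37. The sponsor and the DSMB would therefore see only the approximate version when safety results help in choosing formulations.
3. **The comparison is described as one of dose levels, but the test treats the groups as unordered.** It spends its degrees of freedom on every possible pattern of differences and so has less power against a steady rise with dose.

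**Working it through.** **The plan's own safety figures.** Section 5 gives exact upper bounds for zero events. The formula is 1 − 0.025^(1/n): n = 25 gives 13.7% and n = 150 gives 2.4%. Both reproduce. No power, alpha or expected rate is stated for the solicited-reaction tests, so a two-sided 0.05 level and all reaction rates below are assumptions.

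**When cells become sparse.** The expected count is arm size times pooled rate. 25 × 0.20 = 5 and 20 × 0.25 = 5, so expected counts drop below 5 under about 20% incidence (active arms) or 25% (placebo).

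**Single p-values, five arms (25, 25, 25, 25, 20; N = 120).** With T events and p = T/N, the chi-square statistic is Σ(x − np)²/n divided by p(1 − p), on 4 df. The exact p-value sums ΠC(n, x)/C(120, T) over all tables no more probable than the one observed.

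- *Three events in one active arm.* p = 0.025. Σ(x − np)²/n = 3 × 0.625²/25 + 0.5²/20 + 2.375²/25 = 0.0469 + 0.0125 + 0.2256 = 0.285. Dividing by 0.024375 gives 11.69, p = 0.020. Exact: [4 × C(25,3) + C(20,3)]/C(120,3) = (4 × 2300 + 1140)/280840 = 0.037.
- *Two events in one active arm.* The statistic is 7.73, p = 0.102. Exact: (4 × 300 + 190)/7140 = 0.195.
- *Three in one active arm and one in another.* The statistic is 8.28, p = 0.082. Exact by full enumeration: 0.155.

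If the comparison is read as the three unadjuvanted doses only, the gap can cross 0.05: 0/0/3 of 25 gives 0.044 against 0.102, and 1/2/7 gives 0.028 against 0.066.

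**Type I error of the nominal 5% chi-square test, five arms (simulated).** It is 2.1% at 2% incidence, 3.4% at 5%, 4.4% at 10% and 4.9% at 20%. Full enumeration for three or four arms of 25 gives a maximum of 5.2%. Given a fixed number of events it is erratic: for three arms, 10.3% at 3 events and 0.9% at 5.

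**Power against a rise with dose.** Assumed rates are 20/30/40/50% for placebo, 1, 3 and 10 µg (20, 25, 25 and 25 subjects), by full enumeration except the five-arm row, which is simulated:

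| Test | Power |
|---|---|
| Chi-square, five arms (CpG arm assumed 40%) | 39% |
| Chi-square, four ordered arms | 43% |
| Fisher-Freeman-Halton, four ordered arms | 43% |
| Trend, scores 0, 1, 2, 3 | 61% (exact version 59%) |
| Trend, scores 0, 1, 3, 10 | 53% (exact version 53%) |

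At lower assumed rates the order is the same: 5/10/20/30% gives 52% for four-arm chi-square and 69% for the exact trend test; 4/8/16/24% gives 39% and 57%.

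**The case against.** The strongest reply is that these p-values carry little weight. The safety endpoint is descriptive, Section 5 rests safety on exact bounds, no alpha or rule is attached to the tests, and exact intervals are printed in the same cells. That stands and limits the size of the point. The p-values are still planned, and four of the five tables go to the interim review.

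It can also be said that chi-square is valid on average. It is: a reader might infer from the halved p-values that type I error is inflated, but the test is conservative when events are rare and at most about 5.2% otherwise. The fault lies in individual p-values. Nor does the exact test add power; only using the dose order does.

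Sparsity is an assumption. At about 25% incidence or more, chi-square is adequate. The sparse-table point and the 20 to 50% power scenario therefore concern different reactions, although the trend test keeps its advantage at the lower rates shown.

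The scope is narrower than the whole first primary endpoint. Tables 29, 30 and 34 cover only the 30-minute observation, and the day 1-7 severity tables already use Fisher's exact test.

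Finally, a reader might infer that the trial is built to see reactogenicity rise with dose. Section 3.1 does not support that: it attaches dose-dependence to the neutralizing antibody response and, for safety, asks for an acceptable profile at every dose level. The case for a trend test rests only on Section 8.3.1, which itself describes a comparison of dose levels.

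**Conclusion.** The point holds as a modest correction. The SAP names two tests for parallel analyses, with Tables 30 and 35 in open conflict, and applies the approximate one in five tables with arms of 25 and 20. Where pooled incidence is under about 20 to 25%, which the SAP neither states nor excludes, a chi-square p-value can be about half the exact one. Ignoring dose order costs about 18 points of power in the assumed 20/30/40/50% scenario with equally spaced scores (61% − 43%), or about 16 if the trend test is exact (59% − 43%). With raw-dose scores the gain is about 10 points, so the scores must be fixed in advance. Arms of 25 limit every version. The documents support neither a claim of inflated error nor one that a formal decision depends on these p-values.

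**What to change.** - In Tables 29, 30, 31, 34 and 36, replace chi-square with the Fisher-Freeman-Halton exact test, as in Tables 32, 35 and 37. Name it in Section 8.3.1 so that text and shells agree, and remove the unused note under Table 33.
- State in Section 8.3.1 and the notes whether placebo and the CpG arm enter the overall comparison.
- Add one supportive exact Cochran-Armitage trend test over placebo, 1, 3 and 10 µg without adjuvant, with equally spaced scores 0, 1, 2, 3 fixed before unblinding. The CpG arm has no place in this order and is left out of the trend test.
- Add the overall-dose row that Section 8.3.1 promises, and define it.

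No new data are needed. The cost is more than one EXACT statement per table: a subset for the trend test, a few extra rows, and more p-values with no multiplicity adjustment. Label them descriptive.
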